Planned Sample Size	30 patients (over a maximum 12 month recruitment period).
Follow-up duration	All patients will be followed up as per standard clinical care with repeat examination 1 week, 4 weeks, and 12 weeks after surgery.
Planned Study Period	18 months
Primary Objective	
 • To investigate the efficacy of PuraSinus in reducing patient pain during postoperative debridement after ESS compared to PosiSep X.
Secondary Objectives	
 • To assess the time needed to perform postoperative debridements in patients with PuraSinus in their ethmoid cavity after endoscopic sinus surgery • To assess the efficacy of PuraSinus in preventing postoperative complications from endoscopic sinus surgery (adhesions, bleeding, crusting, edema) • To assess the amount of PuraSinus retained in the ethmoid cavity postoperatively • To assess the need for further intervention postoperatively in patients

Primary Endpoint	
 Patient-reported pain (1-10) during postoperative debridement of ethmoid cavity 1 week after surgery
Secondary Endpoints	
 Time required to perform sinonal cavity debridement for ethmoid cavity 1 week after surgery Postoperative healing assessment of mucosal edema, crusting, secretions, and polyps 1 week, 4 weeks, and 12 weeks using validated Lund-Kennedy scoring rubric. Presence of adhesions at 1 week, 4 weeks and 12 weeks. Severity of bleeding during week 1 debridement Amount of residual PuraSinus or bioresorbable dressing in ethmoid cavity 1 week after surgery The need for further intervention postoperatively 4 weeks after surgery as evaluated by an independent blinded reviewer of the video-endoscopy
Intervention (s)	PuraSinus randomized to one ethmoid cavity after bilateral endoscopic sinus surgery and bioabsorbable nasal dressing to the contralateral ethmoid cavity
Inclusion criteria	
 Patient is 18 years of age or older Patient has a clinical indication for and has consented for primary or revision bilateral ESS and had evidence of ethmoid disease bilaterally (Lund-Mackay score at least 1 on each side). Diagnosed with CRS based on American Academy of Otolaryngology – Head and Neck Surgery guidelines

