PuraSinus is a novel topical hemostatic agent based on a self-assembling peptide nanotechnology in the form of a transparent hydrogel suitable for endoscopic use. In otolaryngology, a case series was published by Ananda in 2017 where PuraSinus was applied to the inferior turbinates in 60 patients who underwent endonasal powered turbinoplasty where results were observed for post-operative re-bleeding and adhesion formation. In all 60 patients, no post-operative re-bleeding was observed and there was no adhesion formation.⁶

The hydrogel form of PuraSinus allows the surgeon to only have to apply a thin layer of the product to the surgical site to achieve its desired hemostatic and wound healing effect. This minimizes the amount of the hydrogel needed to be placed into the ethmoid cavity, which in theory would limit the amount of debridement necessary after surgery leading to minimal patient discomfort.

Therefore, we hypothesize that PuraSinus will have less patient discomfort during postoperative debridement compared to traditional bioresorbable packing. We also hypothesize that PuraSinus will have the same incidence of adhesions, bleeding, crusting, edema as PosiSep X.

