6.0 STRATIFICATION/DESCRIPTIVE FACTORS/RANDOMIZATION SCHEME

6.1 The patient will undergo a bilateral operation. At the end of the surgery, hemostasis will be performed with PosiSep X placed in the ethmoid cavity on one side and PuraSinus in the other ethmoid cavity. The randomization will occur using the envelope method to determine which ethmoid cavity will receive PuraSinus and which ethmoid cavity will receive PosiSep X.

Prior to the start of this trial, a randomization list will be generated and sealed opaque envelopes will be created for each participant in the study. Each envelope will instruct which ethmoid cavity (RIGHT or LEFT) will receive PuraSinus. During the surgery, after a total ethmoidectomy has been performed bilaterally by the surgeon, the research coordinator or research staff will open the assigned envelope and have the surgeon read which side the PuraSinus should be applied to. The contralateral ethmoid cavity will receive PosiSep X. The research staff or research coordinator will verify that the intervention (PuraSinus) was applied to the assigned ethmoid cavity.

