13.0 STATISTICAL CONSIDERATIONS

13.1 Sample size

There are no published data available regarding trial outcomes for the PuraSinus hydrogel product. A study from Canada, reported pain during removal of a comparable bioresorbable packing (Nasopore) as 4.03/10 (SD 2.80) among 30 subjects.⁵ In our clinical practice, PosiSep X bioresorbable packing removal is usually rated approximately 5-6/10 (it is uncomfortable) and PuraSinus removal around a 2/10. Using a mean difference of 2 (4.03 with bioresorbable packing versus 2 with hydrogel), a more conservative SD of 3.5 and testing at a 2-sided alpha=0.05, a sample of 30 subjects will provide 83% power to detect this difference in paired measures using a Wilcoxon signed rank test.

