13.2 Statistical analysis

The sample will be described by demographic and clinical characteristics, summarizing continuous variables by mean (SD) and categorical variable by frequency (percent). All trial outcome comparisons will be tested at a two-sided p-value of 0.05.

Primary objective: To investigate the efficacy of PuraSinus in reducing patient pain during postoperative debridement after endoscopic sinus surgery compared to PosiSep X.

The primary outcome of pain at 1-week debridement, evaluated on a 1-10 scale, will be compared between interventions using a Wilcoxon signed rank test (paired test). The median and interquartile range of the pain score will be summarized for each intervention. To consider side (right/left), a generalized linear mixed effects model will analyze the pain score as a dependent variable, with a random intercept for participant; independent variables will include randomized intervention, side, and an interaction of intervention-by-side (testing if the intervention effect may differ by side).

Secondary objectives:

- To assess the time needed to perform postoperative debridements in patients with PuraSinus in their ethmoid cavity after endoscopic sinus surgery
- To assess the efficacy of PuraSinus in preventing postoperative complications from endoscopic sinus surgery (adhesions, bleeding, crusting, edema)
- To assess the amount of PuraSinus retained in the ethmoid cavity postoperatively
- To assess the need for further intervention postoperatively in patients

Continuously measured secondary trial outcomes (time required for debridement; Lund-Kennedy Endoscopy score) will be compared between interventions using Wilcoxon signed rank and generalize mixed effects model as described above. Amount of bioresorbable dressing retained will be presented as proportions, with 95% confidence intervals (in the categories of none, <50%, ≥50%). Bleeding during debridement and adhesions will be presented as proportions. The need for further intervention will also be presented as proportion (with 95% confidence interval) of participants required further surgical or oral steroid intervention.

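### Section 1.0 expects crusting and edema to match PosiSep X, but Section 13.2 gives the Lund-Kennedy score only difference tests at 0.05, with no confidence interval or margin, and these cannot support that hypothesis.

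*Combined protocol and SAP*

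**What the plan says.** The protocol's Section 1.0, headed as background and hypotheses, states two hypotheses of different kinds. One is less discomfort at debridement, which is a difference. The other is an absence of difference: "We also hypothesize that PuraSinus will have the same incidence of adhesions, bleeding, crusting, edema as PosiSep X".

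Section 13.2 sets one level for everything: "All trial outcome comparisons will be tested at a two-sided p-value of 0.05". For debridement time and the Lund-Kennedy score it says that they "will be compared between interventions using Wilcoxon signed rank and generalize mixed effects model as described above", that is, by the methods written for pain. Section 10.4 lists four Lund-Kennedy items, each graded 0 to 2: polyps, discharge, edema and crusting. It states no total. Adhesions are graded separately as present or absent.

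For two of the four hypothesized complications the plan is descriptive only: "Bleeding during debridement and adhesions will be presented as proportions". Section 13.2 does specify 95% confidence intervals for residual dressing and for further intervention, but none for the Lund-Kennedy score. The documents contain no equivalence or non-inferiority margin and no power figure for any healing outcome. Section 13.1 sizes the trial on pain alone.

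**The concern.** The null hypothesis of the planned Lund-Kennedy test is no difference, which is what Section 1.0 expects to find. A test of difference can contradict that expectation but cannot support it. The one test result consistent with Section 1.0 is p > 0.05, and that result becomes easier to obtain as pairs are lost or grading becomes noisier.

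Section 1.0 also says that a good dressing should serve both comfort and wound healing. If pain is lower and the Lund-Kennedy p-value exceeds 0.05, a report could pair the two and present healing as equal. Without an interval, readers could not see how much worsening the data still allow.

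**Working it through.** **1. The plan's own figure.** Inputs from Section 13.1: difference 2, SD 3.5, 30 subjects, two-sided alpha 0.05, signed-rank test, stated power 83%. Read 3.5 as the SD of the paired difference, so the standardized effect is 2/3.5 = 0.571. Approximate the signed-rank test by a paired t test with n multiplied by 3/pi (its efficiency under normality): 30 × 0.955 = 28.65. The noncentrality is 0.571 × √28.65 = 3.06, and the power is 83.9%. Simulating the signed-rank test gives 84.0%. The stated 83% is reproduced to within about one point, so the same method is used in step 2.

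**2. Lund-Kennedy score, 30 pairs, two-sided 0.05.** The documents give no SD, so express the true worsening d in SDs of the paired difference. Noncentrality = d × √28.65; miss rate = 1 − power.

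| d | noncentrality | miss rate |
|---|---|---|
| 0.2 | 1.07 | 82% |
| 0.3 | 1.61 | 66% |
| 0.4 | 2.14 | 46% |
| 0.5 | 2.68 | 27% |
| 0.6 | 3.21 | 13% |

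Under true equality p > 0.05 occurs about 95% of the time at any sample size. So p > 0.05 is only 0.95/0.66 = 1.4 times as likely under equality as under a 0.3 SD worsening, and 0.95/0.46 = 2.1 times as likely as under a 0.4 SD worsening. That is weak evidence for equality. With 25 pairs, power at 0.5 SD falls from 73% to 65%.

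**3. In points (assumed SDs).** Assume that the four items are summed to 0-8 per side. Simulated totals with a single-side SD of about 1.8 and latent left-right correlations of 0.3 to 0.7 gave mean 95% CI half-widths of 0.57 to 0.85 point. With t(29) = 2.045, SE = half-width/2.045 and SD of the difference = SE × √30. The last two columns are the paired-t miss rate for a true 1-point worsening, and the chance under true equality that the unfavourable CI limit stays below an illustrative 1-point margin, Phi((1 − half-width)/SE).

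| half-width | SE | SD of difference | 1-point worsening missed | limit below 1 point |
|---|---|---|---|---|
| 0.57 | 0.279 | 1.53 | 7% | 94% |
| 0.70 | 0.342 | 1.87 | 19% | 81% |
| 0.80 | 0.391 | 2.14 | 30% | 70% |
| 0.85 | 0.416 | 2.28 | 36% | 64% |

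The signed-rank approximation gives similar values: 7% missed at SD 1.5 and 27% at SD 2. If the SD were 2.5 or 3, it would be 46% or 59%.

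**The case against.** The strongest reply is that the plan never says a non-significant result will be read as equality. A reader might infer such a rule, but Section 13.2 only sets a test level. This stands. What remains is that Section 1.0 states a hypothesis of equality and no section gives a criterion that could support it.

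Second, the formal secondary objective in Sections 2.2 and 13.2 is to assess efficacy in preventing complications, and a difference test suits that. This also stands. The conflict is with the hypothesis in Section 1.0, and rewording that sentence is one way to resolve it.

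Third, the summed score is an indirect measure of the hypothesis. It also contains discharge and polyps, so less discharge could offset worse crusting. This is why the two items should be reported alongside the score.

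Fourth, a reader might conclude that a relevant worsening would often be missed. The documents give no relevant difference, SD or correlation, and under the smaller assumed SDs a 1-point worsening is missed only about 7% of the time. Nor do they give an attrition figure. Weeks 4 and 12 may have fewer pairs, because Section 10.0 requires only week 1 attendance for inclusion in the analysis, but this is not established.

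Finally, the planned mixed model could already produce an estimate with an interval. That is true, but no interval is specified for this score.

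**Conclusion.** The point holds in a limited form. The planned Lund-Kennedy tests cannot support the Section 1.0 hypothesis at any SD, and the plan supplies neither an interval nor a margin that could. That part rests on the text alone. The size rests on assumptions: near-normal paired differences for the miss rates in SD units, and a summed 0-8 score with a paired-difference SD of about 1.5 to 2.3 for the 7% to 36% range in points. The documents do not support the stronger claims that p > 0.05 is a written rule for equality or that important worsening would usually go undetected. The outcome is secondary and the pain analysis is unaffected. The change should be made because it is cheap and prevents an unsupported conclusion.

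**What to change.** In Section 13.2:

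- Report the paired PuraSinus minus PosiSep X difference in the Lund-Kennedy score, and in its crusting and edema items separately, with a 95% CI at weeks 1, 4 and 12. A Hodges-Lehmann interval or the side-averaged contrast from the mixed model would serve for the score.
- State that p > 0.05 will not be read as equality or as no worse healing.

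In Section 1.0, restate the second hypothesis as estimating the difference in healing.

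A margin is optional. If the investigators want to claim that healing is no worse, they should fix a margin and one deciding visit before any outcome data are reviewed, and make the claim only if the unfavourable confidence limit lies within the margin. Unblinding is not a usable deadline, because under Section 6.1 the surgeon learns the allocation in theatre. The 64% to 94% chance shown above for a 1-point margin is an illustration, not a recommended margin.

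The cost is a few sentences, with no new patients or data. The downside is that some results will have to be reported as inconclusive.

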3.0 STUDY DESIGN

3.1 Type of Study

This is a prospective randomized controlled multicenter study at the University of Southern California that will enroll at least 30 participants who satisfy criteria to compare the efficacy of PuraSinus versus standard of care in patients undergoing endoscopic sinus surgery. The study will utilize an intra-patient control design to assess the safety and efficacy of PuraSinus compared to PosiSep X on the contralateral side. The study patients will undergo PuraSinus placement in one nasal cavity following traditional endoscopic sinus surgery. The study is blinded, meaning that patients will be blinded throughout the study duration to which side received PuraSinus placement. The independent surgeon performing review of the video-endoscopies will also be blinded to which side received PuraSinus.

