The study monitor will maintain contact with investigators and study coordinators by phone, email, or on-site visits. Monitoring will be performed concurrently during the period of patient enrollment to completion of the final patient follow-up visit. The frequency of monitoring may occur as often as a biweekly basis. Monitoring will ensure continued protocol compliance and accurate reporting of data, adverse events, protocol deviations and product accountability.

9.0

CLINICAL AND LABORATORY EVALUATIONS AND STUDY CALENDAR

All visits will occur during typical standard of care appointments for patients undergoing endoscopic sinus surgery.

Parameter	Pre-Surgery	Surgery	Week 1	Week 4	Week 12
Sociodemographic Questionnaire, informed consent	X				
Randomization: placement of PuraSinus		X			
Nasal endoscopy video recording			X	X	X
Patient-reported pain during debridement			X		
Endoscopic debridement procedure			X	X ¹	
Time required to perform debridement			X	X ²	
Bleeding			X	X ²	
Review of video-endoscopies by independent blinded surgeon for: 1. Lund-Kennedy score (mucosal edema, crusting, secretions, adhesions, polyps) 2. Residual packing amount 3. Adhesions			X	X	X
Review of video-endoscopy by independent blinded surgeon for: Need for further intervention				X	
Ascertainment of side effects and adverse events		X	X	X	X

Table 1. Study Calendar

¹if clinically indicated.

²if debridement performed

10.0

CRITERIA FOR EVALUATION AND ENDPOINT DEFINITIONS

The outcome status of all eligible patients will be reported. All eligible patients who begin treatment and attend the week 1 postoperative visit will be included in the analysis.

ENDPOINT DEFINITIONS

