10.3 Bleeding During Debridement

The patient will be evaluated during the postoperative week 1 for bleeding during debridement via a recorded nasal endoscopy that will be evaluated by a blinded reviewer. Bleeding will also be assessed at week 4 if a second debridement is performed. The reviewer will grade bleeding during after debridement with the following scale:

Criteria	0	1	2	3
Bleeding	No bleeding	Minimal (confined to the nasal cavity)	Moderate (out of nasal cavity)	Severe (needs repacking or cauterization)

10.4 Postoperative healing assessment of mucosal edema, crusting, secretions, adhesions, and polyps

Nasal endoscopies will be recorded of each participant's ethmoid cavity at 1 week, 4 weeks, and 12 weeks and will be reviewed by a blinded reviewer to evaluate the healing of the ethmoid cavity. The reviewer will assess mucosal edema, crusting, secretions, and polyps using the validated Lund-Kennedy Endoscopy score. Adhesions will be evaluated as either present or absent in the middle meatus.

Criteria	0	1	2
Polyps in middle meatus	Absent	Restricted to middle meatus	Beyond the middle meatus
Discharge in middle meatus	Absent	Thin and clear discharge	Thick and purulent
Edema of the middle meatus	Absent	Mild-moderate	Moderate-severe
Crusting in middle meatus	Absent	Mild-moderate	Moderate-severe

Lund-Kennedy Endoscopy score

Criteria	0	1
Adhesions	No adhesion	Present in middle meatus

Adhesions Criteria

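### Adhesions and bleeding are planned only as side-by-side proportions, with no paired between-side difference or interval, although the design is within-patient and Section 1 hypothesises equal incidence

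*Combined protocol and SAP*

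**What the plan says.** Section 1.0 states: "We also hypothesize that PuraSinus will have the same incidence of adhesions, bleeding, crusting, edema as PosiSep X". Section 3.1 sets the comparison within patients: "The study will utilize an intra-patient control design to assess the safety and efficacy of PuraSinus compared to PosiSep X on the contralateral side". Section 2.2, repeated in 13.2, makes prevention of these complications a secondary objective.

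Section 13.2 then treats the outcomes unequally:

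- **Debridement time and Lund-Kennedy score:** "Continuously measured secondary trial outcomes (time required for debridement; Lund-Kennedy Endoscopy score) will be compared between interventions using Wilcoxon signed rank", plus a mixed effects model with intervention and side as terms.
- **Residual dressing and need for further intervention:** proportions with 95% confidence intervals.
- **Adhesions and bleeding:** "Bleeding during debridement and adhesions will be presented as proportions", and nothing more.

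A general sentence adds: "All trial outcome comparisons will be tested at a two-sided p-value of 0.05". It names no method for a paired binary or ordinal outcome.

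On the outcomes themselves, Section 10.4 says: "Adhesions will be evaluated as either present or absent in the middle meatus". The synopsis lists adhesions at weeks 1, 4 and 12. Section 10.3 has the blinded reviewer grade bleeding from 0 to 3 at week 1, and adds: "Bleeding will also be assessed at week 4 if a second debridement is performed".

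**The concern.** In a split-sided trial, the information about a between-side difference in a yes/no outcome lies in the discordant pairs: patients affected on one side only. Two marginal proportions do not reveal how many there were, so a reader cannot rebuild a valid interval from them. If the report shows two similar percentages beside a stated expectation of equal incidence, readers will be inclined to take the expectation as confirmed, with nothing to show how large an excess on the PuraSinus side the data still permit.

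This matters because the primary hypothesis is less pain with PuraSinus, and the complications hypothesis says that the benefit comes without more adhesions or bleeding. Weighing the two needs an estimate of the complication difference and its uncertainty.

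**Working it through.** **1. The plan's own figure.** The only power figure, in Section 13.1, is 83% for pain (30 subjects, difference 2, SD 3.5, two-sided 0.05, Wilcoxon signed rank). Reading 3.5 as the SD of the paired difference, paired noncentral t power with n multiplied by 3/π gives 83.9%, and simulation gives 84.0%. The figure reproduces within about one point, but it concerns pain only. No complication outcome was sized.

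**2. Inputs.** n = 30 pairs (Section 13.1). The documents give no usable comparative complication rates. Section 1.0 cites no re-bleeding and no adhesions in 60 patients, but that was turbinoplasty with no PosiSep X side. All counts below are therefore assumptions.

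**3. Marginal proportions do not fix the interval.** Let b be the patients affected on the PuraSinus side only, and c those affected on the PosiSep X side only. The paired difference is (b − c)/n. An observed 3/30 v 3/30 is compatible with b = c = 0, 1, 2 or 3.

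The Tango score limits are the values D at which |T(D)| = 1.96, where

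- T(D) = (b − c − nD) / √{n[2q + D(1 − D)]}
- q = [√(B² − 4AC) − B] / (2A), with A = 2n, B = −b − c + (2n − b + c)D, C = −cD(1 − D).

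With no discordant pairs this reduces to z²/(n + z²) = 3.8415/33.8415 = 0.1135.

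With b = c = 3, at D = 0.1817: B = −6 + 60 × 0.1817 = 4.902; C = −3 × 0.1817 × 0.8183 = −0.446; q = (11.449 − 4.902)/120 = 0.0546; variance = 30 × (0.1091 + 0.1487) = 7.734; T = −5.451/2.781 = −1.96. The limit is therefore 0.182.

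| Observed | b + c | Tango 95% CI (points) |
|---|---|---|
| 3/30 v 3/30 | 0 + 0 | −11.4 to +11.4 |
| 3/30 v 3/30 | 1 + 1 | −14.0 to +14.0 |
| 3/30 v 3/30 | 2 + 2 | −16.2 to +16.2 |
| 3/30 v 3/30 | 3 + 3 | −18.2 to +18.2 |
| 6/30 v 3/30 | 3 + 0 | −2.5 to +25.6 |
| 6/30 v 3/30 | 6 + 3 | −10.6 to +30.3 |

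The interval depends on b, c and n, not on the marginal rates beyond their difference. More discordance widens it. With b = c = 5, at D = 0.2155: B = 2.93, C = −0.845, q = 0.0968, variance = 30 × (0.1935 + 0.1691) = 10.88, T = −6.465/3.298 = −1.96, giving ±21.5 points. That much discordance is possible for any-grade bleeding, where grade 1 is minimal bleeding.

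**4. If the general 0.05 sentence were applied.** The plan names no test here; exact McNemar is an assumption. With all k discordant pairs in one direction, p = 2 × 0.5^k: k = 5 gives 0.0625 and k = 6 gives 0.031. Five or fewer discordant pairs can never reach significance. For an assumed true 20% v 10%, exact McNemar power with 30 pairs is 7.3%, 9.9% and 9.2% at discordant shares of 10%, 20% and 30%. Under those assumptions a doubling would be non-significant in about nine trials of ten, so non-significance could not be read as sameness.

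**5. Which complications are affected.** Crusting and edema are items of the Lund-Kennedy table in Section 10.4. That score gets a paired Wilcoxon test and a mixed model whose intervention term estimates a between-side effect, on a score rather than an incidence. Adhesions and bleeding have no counterpart.

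**6. A side inconsistency.** Table 1 in Section 9.0 has the blinded surgeon review "Lund-Kennedy score (mucosal edema, crusting, secretions, adhesions, polyps" and then lists adhesions again as a separate item. Section 10.4 and the synopsis keep adhesions outside the score. Even if they were inside, a composite score would not yield adhesion incidence.

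**The case against.** The best defence is that equal incidence is mentioned once, in the background, while the formal objective is to assess prevention of complications. No equivalence or non-inferiority conclusion is planned and no margin is set. Descriptive reporting of secondary complications is defensible in a 30-patient trial sized for pain. Both sides are graded in every patient, so paired results could be produced later. The assumed 10% and 20% rates are illustrative and may not fit any-grade bleeding.

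Most of this stands, and it limits the point. A reader might infer that the trial intends a formal equivalence claim with an invalid analysis. The documents do not support that, and no margin is required. A reader might also infer that all four complications lack a between-side analysis. They do not, because the Lund-Kennedy model can estimate an effect for the score that includes crusting and edema.

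What remains is that descriptive reporting in a paired design still needs the paired estimate. The same paragraph of 13.2 gives intervals or paired methods to its other secondary outcomes. That the data could be paired later does not commit anyone to doing so.

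**Conclusion.** The point holds for adhesions and bleeding. The stated method gives no paired difference and no interval for an objective that is comparative and within-patient. At 30 pairs, equal observed rates would leave differences of about 11 to 18 points compatible with the data for zero to six discordant pairs, and more with greater discordance. These widths rest on assumed counts, complete pairs and the Tango method.

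Neither similar proportions nor a non-significant test could establish equal incidence. The plan should be changed here, but the gap does not threaten the trial: the primary pain analysis is unaffected. The Table 1 discrepancy is minor and does not cause the gap.

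**What to change.** In Section 13.2, replace the sentence on bleeding and adhesions with the following:

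- **Adhesions at weeks 1, 4 and 12:** the paired risk difference (PuraSinus minus PosiSep X) with a matched-pairs 95% interval (for example Tango) and both discordant-pair counts, among patients with both sides graded at that visit.
- **Bleeding at the week 1 debridement:** grades 0 to 3 by side, and a paired between-side difference with 95% interval at a cut-point stated in advance (for example grade 1 or more, since grade 0 in Section 10.3 is no bleeding). Summarise week 4 bleeding descriptively where a second debridement was done.
- **Interpretation:** state that the Section 1 similarity hypothesis is descriptive, and that similar proportions or a non-significant result will not be reported as the same incidence.

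Separately, reconcile Table 1 with Section 10.4 on whether adhesions belong to the Lund-Kennedy score.

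The cost is SAP wording, one table correction and a few output rows from data already being collected. The downside is a more modest complications claim with visibly wide intervals. Sample size and the primary analysis do not change.
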